6.7.1. Permitted Medications and Procedures

6.7.1.1. Pneumocystis jirovecii Pneumonia Prophylaxis

All participants will receive a PJP prophylaxis regimen determined by the investigator. Examples of standard PJP prophylaxis therapies include trimethoprim-sulfamethoxazole, atovaquone, dapsone with or without pyrimethamine, and pentamidine (National Comprehensive Cancer Network 2017). Due to reports of cross-sensitivity between sulfonamides and dapsone, all participants who have a known or suspected allergy to sulfonamides must receive either inhaled pentamidine or atovaquone for PJP prophylaxis. If inhaled pentamidine or atovaquone are not available, the participants should not be enrolled. Prophylaxis should be given while participants are receiving study drug and should continue for at least 2 to 6 months after the last dose of study drug.

The prophylactic agents will be obtained from commercial supplies and will be reimbursed by the sponsor. Investigators are responsible for ensuring that participants receive commercially available supplies of the selected prophylactic agents as required per Protocol. The sponsor may provide prophylactic agents where required by applicable law or regulation or under other limited circumstances when a participant may not otherwise have access to these therapies. The contents of the label will be in accordance with all applicable regulatory requirements. Further details are available in the Pharmacy Manual.

6.7.1.2. Folic Acid, Vitamin B12, or Iron Deficiencies

Participants who are noted to be deficient in folic acid, vitamin B12, or iron should have replacement determined by the investigator as per current standard of care.

6.7.2. Restricted Medications and Procedures

Restricted medications and procedures include the following:

- Use of systemic corticosteroid doses ≤ 20 mg/day prednisone (or equivalent) is permitted from the 14 days before the baseline visit through the EOT visit. Prednisone (or equivalent) should remain stable and may be tapered if the investigator considers it appropriate based on the participant's clinical response.
- Short courses of systemic corticosteroid doses > 20 mg/day prednisone (or equivalent) are permitted (eg, for the treatment of severe or life-threatening AEs) but are otherwise discouraged from the screening visit through the EOT visit.
- Use of weak or moderate inducers or inhibitors of CYP3A4 or P-glycoprotein is discouraged, and investigators should seek other options where possible.

6.7.3. Prohibited Medications and Procedures

Prohibited medications and procedures include the following:

• Use of potent inducers and inhibitors of CYP3A4 is prohibited, with the exception of topical ketoconazole because of its low bioavailability.

• Apart from the study treatments, the use of any medications as described in the exclusion criteria (see Section 5.2) through the safety follow-up is prohibited.

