2.3. Current Treatment and Unmet Need in Autoimmune Hemolytic Anemia

Currently there is no approved and effective targeted therapy for treatment of AIHA. For wAIHA, corticosteroids remain the first-line therapy; however high initial doses are required, responses are often achieved slowly, and only a minority of patients (< 20%) achieve a lasting response (< 20%; Barcellini et al 2014). Since most RBC destruction occurs in the spleen in wAIHA, it is not surprising that splenectomy is a reasonably efficient second-line treatment with a sustained response rate of 60% to 70%. In the third-line situation, immunosuppressive drugs such as danazol, azathioprine, cyclophosphamide, or cyclosporine are used, although response rates are poorly documented, and most publications are single case reports or small retrospective studies. In contrast to wAIHA, only 14% of CAD patients have responses to corticosteroids, and other unspecific immunosuppressive drugs have little efficacy. As CAD is usually not a primary disease, recommended first-line therapy is to treat the underlying disease.

Rituximab is a chimeric monoclonal antibody that targets CD20 antigen on B lymphocytes. By binding to CD20, it induces apoptosis of CD20-positive B cells. Rituximab has recently been licensed in rheumatoid arthritis and is also widely used off-label in various autoantibody-mediated autoimmune diseases, such as immune thrombocytopenic purpura and systemic lupus erythematosus. Recently, rituximab has been considered as second-line therapy for wAIHA and first-line therapy for CAD. Second-line treatment with rituximab leads to response rates similar to splenectomy (~70%), but rituximab-induced responses seem less sustained, and relapses are frequent. Major concerns regarding the adverse effects from rituximab are related to long-lasting B-cell suppression and include increased risk of infection including hepatitis B reactivation (Artz et al 2010) and possibly PML (Carson et al 2009).

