5.1. Inclusion Criteria

A participant who meets all of the following criteria may be included in the study:

- 1. Men or women, aged 18 years or older.
- 2. Diagnosis of AIHA based on the presence of hemolytic anemia and serological evidence of anti-erythrocyte antibodies, detectable by the DAT as follows:
 - a. Warm: DAT positive for IgG only or IgG plus C3d
 - b. Cold (CAD): DAT positive for C3d only, with cold agglutinins of I specificity
 - c. Mixed: DAT positive for IgG and C3d, with coexistence of warm autoantibodies and high titer cold agglutinins
- 3. Participants who have disease progression after treatment with standard therapies that are known to confer clinical benefit or who are intolerant to treatment. There is no limit to the number of prior treatment regimens.
- 4. Hemoglobin 7 to 10 g/dL (as determined by local laboratory).
- 5. No evidence of a lymphoproliferative malignancy or other autoimmune-related underlying conditions (eg, systemic lupus erythematosus, Castleman's disease, Sjögren's syndrome, or other autoimmune diseases).

- 6. ECOG performance status score of 0 to 2 (see Appendix C and Oken et al 1982).
- 7. Willingness to avoid pregnancy or fathering children based on the criteria below:
 - a. Woman of nonchildbearing potential (ie, surgically sterile with a hysterectomy and/or bilateral oophorectomy OR postmenopausal, defined by last menstrual period > 12 months before screening and confirmed by FSH).
 - b. Woman of childbearing potential who has a negative serum pregnancy test at screening and who agrees to take appropriate precautions to avoid pregnancy (with at least 99% certainty) from screening through at least 93 days after the last dose of study drug. Permitted methods that are at least 99% effective in preventing pregnancy (see Appendix A) should be communicated to the participant and her understanding confirmed.
 - c. Man who agrees to take appropriate precautions to avoid fathering children (with at least 99% certainty) from screening through at least 93 days after the last dose of study drug. Permitted methods that are at least 99% effective in preventing pregnancy (see Appendix A) should be communicated to the participant and his understanding confirmed.
- 8. Able to comprehend and willing to sign an ICF.
- 9. Willingness to receive PJP prophylaxis during the study period.

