- 9. History or presence of an abnormal ECG that, in the investigator's opinion, is clinically meaningful. Participants with screening QTc interval > 470 milliseconds for males and > 480 milliseconds for females (corrected by Fridericia) are excluded. In the event that a single QTcF is > 470 milliseconds for males or > 480 milliseconds for females, the participant may enroll if the average QTcF for 3 ECGs is < 470 milliseconds for males or < 480 milliseconds for females.

10. Use of the following medications:

- a. Treatment with rituximab within 3 months of the baseline visit.
- b. Use of immunosuppressive therapy within 28 days of the baseline visit. Immunosuppressive therapy includes, but is not limited to, cyclosporine A, tacrolimus, or high-dose corticosteroids. Participants receiving corticosteroids must be at a dose level ≤ 20 mg/day (prednisone or equivalent corticosteroid dose) within 14 days of the baseline visit.
- c. Chronic or current active infectious disease requiring systemic antibiotics, antifungal, or antiviral treatment or exposure to a live vaccine within 28 days of the baseline visit.
- d. Use or expected use during the study of any prohibited medications, including potent CYP3A4 inhibitors or inducers within 14 days or 5 half-lives (whichever is longer) before the baseline visit.
- e. Current treatment or treatment within 30 days or 5 half-lives (whichever is longer) before the baseline visit with another investigational medication, or current enrollment in another investigational drug protocol.
- f. Use of any prohibited medications (see Section 6.7.3) within 14 days or 5 half-lives (whichever is longer) before the baseline visit.
- 11. Known hypersensitivity or severe reaction to INCB050465 or its excipients (IB).
- 12. Unable to swallow oral medication, malabsorption syndrome, disease significantly affecting gastrointestinal function, total resection of the stomach or small bowel, ulcerative colitis, symptomatic inflammatory bowel disease, or partial or complete bowel obstruction.
- 13. Current alcohol or drug use that, in the opinion of the investigator, will interfere with the participant's ability to comply with the dose regimen and study evaluations.

- 14. Participants who, in the opinion of the investigator, are unable or unlikely to comply with the dose regimen and study evaluations.

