6.4. Exposure

For participants in the FAS and TE, descriptive statistics will be provided for duration of treatment, average daily dose, and total dose separately. Duration of treatment with INCB050465 is defined as the number of days from Day 1 to the date of last record of INCB050465 administration. In addition, daily usage of prednisone (or equivalent) will be summarized using descriptive statistics.

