7.2. Efficacy Parameters

A CR for a given visit is attained if the following 2 conditions are satisfied:

1. Hemoglobin ≥ 12 g/dL.
2. Last transfusion occurred > 1 week before the date of visit.

A PR for a given visit is achieved if the following 2 conditions are satisfied:

1. Hemoglobin 10-12 g/dL or ≥ 2 g/dL increase from baseline.
2. Last transfusion occurred > 1 week before the date of visit.

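### SAP 7.2 screens response for recent transfusion but not for corticosteroid use, so a hemoglobin rise during or soon after a permitted course above 20 mg/day counts as a response to study drug

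*Protocol*

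**What the plan says.** **Response definition.** SAP 7.2 sets two conditions for each response category at a visit. One is hemoglobin: at least 12 g/dL for CR; 10-12 g/dL, or a rise of at least 2 g/dL from baseline, for PR. The other is "Last transfusion occurred > 1 week before the date of visit". SAP 7.3 counts a participant who meets the definition at any one visit from Week 6 to Week 12. SAP 5.3.1 uses the full analysis set (FAS) for all efficacy analyses.

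**Steroid rules.** Under Protocol 6.7.2, doses up to 20 mg/day are allowed and should stay stable or be tapered. Short courses above that "are permitted (eg, for the treatment of severe or life-threatening AEs) but are otherwise discouraged from the screening visit through the EOT visit". No dose or day limit is given. Section 6.7.3 adds that, study treatment apart, "the use of any medications as described in the exclusion criteria (see Section 5.2) through the safety follow-up is prohibited". Criterion 10b in Section 5.2 reads: "Immunosuppressive therapy includes, but is not limited to, cyclosporine A, tacrolimus, or high-dose corticosteroids". It goes on to say that participants on corticosteroids "must be at a dose level ≤ 20 mg/day (prednisone or equivalent corticosteroid dose) within 14 days of the baseline visit".

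**Why steroids bear on the endpoint.** For warm AIHA, Protocol 2.3 says that "corticosteroids remain the first-line therapy; however high initial doses are required, responses are often achieved slowly".

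**What is planned for steroid data.** SAP 6.4 says that "daily usage of prednisone (or equivalent) will be summarized using descriptive statistics". SAP 7.4 makes prednisone use a secondary endpoint, with a by-visit table (2.2.7) and a listing (2.3). None of these feeds into responder status.

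**The concern.** The plan accepts that a hemoglobin rise can have a cause other than study drug and screens out one such cause, transfusion. It does not screen out the other cause that its own background section makes prominent. Neither cohort has a control group, so nothing in the design shows how much of an observed response belongs to steroids. The any-visit rule makes one qualifying visit enough, so the bias runs upward.

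The reported rates matter beyond this study. SAP 10.1 says the analysis after Week 12 is meant to support publications and a possible Phase 3 plan for participants with cold agglutinin disease (CAD). No planned output ties steroid use to response. If someone later wanted to discount a responder, the rule would have to be written with open-label data in view.

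**Working it through.** **1. The plan's one numeric design figure.** Protocol 10.1 gives the chance of seeing at least one adverse event of interest at a true rate of 20%. The formula is 1 - (1 - rate)^n. For n=10: 1 - 0.8^10 = 0.893. For n=15: 1 - 0.8^15 = 0.965. Both match the stated figures (above 89% and above 96%). The present point does not rest on them.

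**2. Does any rule stop a steroid-driven rise from counting?**

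| Place | Content | Changes responder status? |
|---|---|---|
| SAP 7.2 | Hemoglobin; transfusion more than 1 week earlier | No steroid condition |
| SAP 7.3 | Any one visit, Week 6 to 12 | No |
| SAP 5.3.1 | FAS for all efficacy; no per-protocol set defined | No |
| SAP 6.3 | Deviations listed; major ones tabulated | No |
| SAP 6.4, 7.4, Table 2.2.7, Listing 2.3 | Prednisone use described | No |

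So a qualifying hemoglobin at a Week 6 to 12 visit, more than a week after any transfusion, counts whatever the steroid dose.

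**3. Effect of one misattributed responder,** 100/n points: 100/10 = 10.0 (Cohort 1); 100/15 = 6.7 (Cohort 2); 100/25 = 4.0 (overall).

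**4. Chance of at least one.** The documents give no rate. Assume a share q of participants has a response reached only with such a course. The chance of at least one is 1 - (1 - q)^n:

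| Assumed q | n=10 | n=15 | n=25 |
|---|---|---|---|
| 2% | 18% | 26% | 40% |
| 5% | 40% | 54% | 72% |
| 10% | 65% | 79% | 93% |

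These values of q are illustrations, not estimates.

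**5. Response visits that a look-back removes.** Take nominal visits at Days 42, 56, 70 and 84. With look-back w, visit v is removed if any course day d satisfies v - w ≤ d ≤ v. For one course of 1 to 7 days lying wholly between two adjacent visits:

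| Course between | w = 14 | w = 28 |
|---|---|---|
| Weeks 2 and 4 | none | Week 6 |
| Weeks 4 and 6 | Week 6 | Weeks 6, 8 |
| Weeks 6 and 8 | Week 8 | Weeks 8, 10 |
| Weeks 8 and 10 | Week 10 | Weeks 10, 12 |
| Weeks 10 and 12 | Week 12 | Week 12 |

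The ±3-day visit windows widen this, as three examples show:
- w = 14, Week 8 on Day 53 and Week 10 on Day 73: a course on Days 54-58 removes no visit, because the Week 10 look-back starts on Day 59.
- w = 14, Week 10 on Day 73 and Week 12 on Day 81: a course on Days 67-72 removes both, because the look-backs start on Days 59 and 67.
- w = 28, Weeks 6, 8 and 10 on Days 45, 56 and 67: a course on Days 40-44 removes all three, because the look-backs start on Days 17, 28 and 39.

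**The case against.** **The route to bias is narrow.** Entry criterion 3 admits "Participants who have disease progression after treatment with standard therapies that are known to confer clinical benefit or who are intolerant to treatment", so many participants will already have done poorly on steroids. Protocol 2.3 calls steroid responses slow and puts the steroid response rate in CAD at 14%. About 5 of about 15 Cohort 2 participants are planned to have CAD. The one stated example of a high-dose course is a severe or life-threatening adverse event, and Table 4 of the protocol stops study drug for other Grade 4 toxicity. That leaves few on-treatment visits in the window after such an event. All of this stands and limits the bias. It does not remove it: the adverse-event use is only an example, other use is discouraged rather than barred, and at least 7 of the 10 Cohort 1 participants are to have warm disease.

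**The study is exploratory and small.** No hypothesis is tested. A reader of the hemoglobin, prednisone, concomitant medication and adverse event listings could trace a responder's steroid course. That is true, but tracing does not change the reported rate, and no rule says how to treat what is found. No reclassification is planned either.

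**Stronger readings that the documents do not support:**
- *That 6.7.2 and 6.7.3 flatly contradict each other.* Criterion 10b is a pre-baseline window and gives no number for a high dose. Section 6.7.2 is the specific permission, and 6.6.2 also lets investigators use whatever medication is needed, after discussion with the sponsor where possible. What is missing is a statement of precedence. The response gap would remain even with that supplied.
- *That the SAP amendment created the gap by dropping the hemolysis-marker condition.* The protocol's own CR and PR definitions have no steroid condition, and marker normalization would not exclude a steroid-driven remission.
- *That the response rates are in fact inflated.* Nothing shows how often such courses occur, and the points per responder apply to any misclassification.

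**Conclusion.** The gap in the response definition is real: following the plan as written, a hemoglobin rise during or soon after a permitted course above 20 mg/day counts as a response. The direction is upward and the size is unknown. Each case is worth 10.0, 6.7 or 4.0 points, taking the planned cohort sizes as the FAS denominators. The concern rests on the protocol's own account of steroids as active in warm AIHA and applies mainly to that type.

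The same question arises when a dose is raised above baseline but stays at or below 20 mg/day. Section 6.7.2 advises a stable dose, yet SAP 7.2 would still count the visit. The wording of 6.7.3 is a minor matter of clarity.

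**What to change.** 1. **SAP 7.2 and 7.3.** Keep the current primary analysis. Prespecify beside it a sensitivity analysis of CR and PR. In it, a visit is not a response visit if, within a set look-back, systemic corticosteroid exceeded 20 mg/day prednisone equivalent or was raised above the participant's baseline dose. For example, use 28 days and repeat with 14. These lengths appear in criterion 10b as eligibility windows, not as durations of steroid effect, so the final choice is clinical. The participant stays in the FAS denominator.
2. **Listings 2.1 and 2.3.** Flag responders who had such use.
3. **Protocol 6.7.3, second bullet.** Add an exception for systemic corticosteroids as allowed in Section 6.7.2.

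**Cost.** One derivation, one flag and one clause. Prednisone-equivalent use and concomitant medications are already recorded, and eligibility does not change. The downside is that true response visits can be lost in the sensitivity version. For a short course between adjacent visits from Week 4 on, the loss on nominal days is 1 of 4 visits at 14 days (0 to 2 with the visit windows) and 1 to 2 of 4 at 28 days (up to 3 in the example above). A course between Weeks 8 and 10 would remove Weeks 10 and 12 at 28 days, when a Cohort 1 participant escalated between Weeks 6 and 8 might be responding. Both versions should therefore be reported.

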7. DISCONTINUATION OF STUDY TREATMENT AND PARTICIPANT DISCONTINUATION/WITHDRAWAL

7.1. Discontinuation of Study Treatment

The decision to discontinue study drug will not constitute study completion. In the event that study drug is discontinued, the treatment period will be considered complete, and the follow-up period will begin.

7.1.1. Permanent Discontinuation of Study Treatment

Participants **must** be withdrawn from study drug for the following reasons:

- The participant becomes pregnant.
- Consent is withdrawn.

Note: Consent withdrawn means that the participant can no longer be followed. Participants may choose to discontinue study drug and remain in the study to be followed.

- Further participation would be injurious to the participant's health or well-being, in the investigator's medical judgment.
- The study is terminated by the sponsor.
- The study is terminated by the local health authority, IRB, or IEC.

A participant **may** be discontinued from study drug as follows:

- If, during the course of the study, a participant is found not to have met eligibility criteria, the medical monitor, in collaboration with the investigator, will determine whether the participant should be withdrawn from the study.
- If a participant is noncompliant with study procedures or study drug administration in the investigator's opinion, the sponsor should be consulted for instruction on handling the participant.

7.1.2. Discontinuation Procedures

In the event that the decision is made to permanently discontinue the study drug, the EOT visit should be conducted. Reasonable efforts should be made to have the participant return for follow-up visits. These visits are described in Table 1. The last date of the last dose of study drug and the reason for discontinuation of study drug will be recorded in the eCRF.

If a participant is discontinued from study drug:

- The study monitor or sponsor must be notified.
- The reason(s) for withdrawal must be documented in the participant's medical record and in the eCRF.
- The EOT visit should be performed.
- The date of the EOT visit should be recorded in the IRT system.
- Participants must be followed for safety until the time of the follow-up visits or until study drug-related toxicities resolve, return to baseline, or are deemed irreversible, whichever is longest.

If the participant discontinues study drug and actively withdraws consent for collection of follow-up data (safety follow-up or disease assessment), then no additional data collection should occur; however, participants will have the option of withdrawing consent for study drug but continuing in the follow-up period of the study for safety/efficacy assessments (see Section 8.9).

7.2. Participant Withdrawal From the Study

A participant may withdraw from the study at any time at his or her own request or may be withdrawn at any time at the discretion of the investigator for safety, behavioral, compliance, or administrative reasons.

If a participant withdraws consent for disclosure of future information, the sponsor may retain and continue to use any data collected before such a withdrawal of consent.

If a participant withdraws from the study, he or she may request destruction of any samples taken and not tested, and the investigator must document this in the site study records.

See Table 1 for data to be collected at the time of study discontinuation and follow-up and for any further evaluations that need to be completed.

7.3. Lost to Follow-Up

A participant will be considered lost to follow-up if he or she repeatedly fails to return for scheduled visits and is unable to be contacted by the study site.

The following actions must be taken if a participant fails to return to the clinic for a required study visit:

- The site must attempt to contact the participant and reschedule the missed visit as soon as possible and counsel the participant on the importance of maintaining the assigned visit schedule and ascertain whether or not the participant wishes to and/or should continue in the study.
- Before a participant is deemed lost to follow-up, the investigator or designee must make every effort to regain contact with the participant (where possible, 3 telephone calls and, if necessary, a certified letter to the participant's last known mailing address

- or local equivalent methods). These contact attempts should be documented in the participant's medical record.
- Should the participant continue to be unreachable, he or she will be considered to have withdrawn from the study with a primary reason of lost to follow-up.

